5. TREATMENT OF SUBJECTS

5.1. Investigational product/treatment

Anidulafungin

Detailed information on anidulafungin, the investigational product used in this study can be found in the SPC. A short summary is given here. The information currently available on combination therapy with a triazole and an echinocandin for the treatment of IA is described below (6.2).

Mechanism of action

Anidulafungin is a semi-synthetic echinocandin, a lipopeptide synthesised from a fermentation product of Aspergillus nidulans. Anidulafungin selectively inhibits 1,3-8-D glucan synthase, an enzyme present in fungal, but not mammalian cells. This results in inhibition of the formation of 1,3-beta-D-glucan, an essential component of the fungal cell wall. Anidulafungin has shown fungicidal activity against Candida species and activity against regions of active cell growth of the hyphae of Aspergillus fumigatus.

Chemical Name

Anidulafungin has the chemical name 1-[(4R,5R)-4,5- Dihydroxy-N2- [[4"-(pentyloxy) [1,1':4',1"-terphenyl]- 4- yl]carbonyl]- Lornithine]echinocandin B.

Name of medicinal product

ECALTA 100 mg powder for concentrate for solution for infusion

Method of administration

For intravenous use only.

ECALTA should be reconstituted with water for injections to a concentration of 3.33 mg/mL and subsequently diluted to a concentration of 0.77 mg/mL.

Dosage & duration

Adult patients receive a loading dose on day-1 of 200mg IV, followed by 100 mg daily thereafter.

Anidulafungin will be given for at least 7 days but no longer than 28 days. Please note that this refers to the MITT primary endpoint population. In patients in which triazole resistance is demonstrated or in which the results of the resistance test are inconclusive, the treatment duration of combination therapy can be much longer. These patients are not included in the MITT primary endpoint population.

Intervention

Treatment with a triazole (voriconazole or isavuconazole or posaconazole) + anidulafungin IV. The triazole is administered for at least 6 weeks while anidulafungin is given for at least 7 and a maximum of 28 days.

Comparator

Treatment with a triazole (voriconazole or isavuconazole or posaconazole) for at least 6 weeks.

In both groups, the route of administration is according to the choice of the treating physician as well as the decision to perform or not perform therapeutic drug monitoring of the triazole drug.

5.2. Use of co-intervention (if applicable)

Not applicable

5.3. Resistance testing

At the end of 2017, the Dutch SWAB guideline on the treatment of invasive fungal infections was updated. To take the increasing incidence of triazole resistance in the Netherlands into account, this guideline describes 2 preferred treatment strategies for patients with invasive aspergillosis. One strategy is to start with combination therapy (azole in combination with echinocandin or azole with liposomal amphotericin-B) until resistance test results become available. This is an option for critically ill patients or in

a setting where real-time resistance testing is not readily available. In a setting where real-time and state-of-the-art resistance testing is available, treatment with triazole monotherapy is recommended as an alternative strategy.

To allow for the treatment with triazole monotherapy in the Dutch patient population of this study, resistance testing will be done in all patients included in the Netherlands at the study site or at Erasmus MC if not part of the standard local diagnostic work-up. Furthermore, all Belgian sites in which triazole resistance testing is not the current standard of care, will be given the opportunity to send BAL samples to a central lab in Belgium (UZ Leuven or AZ Sint-Jan in Brugge) for real-time resistance testing free of charge. All participating centers will also receive the lab tools to perform in-house phenotypic resistance testing using VIPcheckTM free of charge (see below).

Resistance testing will be performed using a combination of phenotypic as well as genotypic resistance tests. Phenotypic resistance testing means that the fungus is cultured in the presence and absence of triazole drugs to observe suppression of growth in the presence of triazole drugs. It is currently certainly not the standard of care diagnostic procedure in all Belgian centers. Centers where this is not a standard procedure will receive the necessary tools to implement phenotypic resistance testing with the use of the VIPcheck™. This test was developed and validated by Radboud UMC. 6,14 The VIPcheck™ is a test consisting out of a 4-well plate in which three of the four wells contain agar supplemented with an azole (voriconazole, itraconazole and posaconazole) and the fourth functions as a growth control. If an Aspergillus strain grows in a well with an azole, it is very likely that this strain is azole-resistant. This test will be performed locally at the sites where this is the standard of care and the presence of resistance will be confirmed with the European Committee on Antibiotic Susceptibility Testing (EUCAST) method at the reference mycology lab of the Netherlands or Belgium (Radboud UMC and UZ Gasthuisberg Leuven). Sites that are currently not using the VIPcheck but are willing to use it can contact the study team to get the test sent to them. Genotypic resistance testing means that a PCR test is used to document the absence or presence of certain mutations in the DNA of the fungus that are known to result in phenotypic resistance. For this purpose, 1.5 to 2ml of the BAL sample of each patient will be submitted to the central lab to test for the presence of with the commercially available AsperGenius[®]. This PCR allows for the simultaneous detection of Aspergillus species and identification of the most common mutations circulating in Belgium and the Netherlands (TR34/L98H or TR₄₆/T289A/Y121F) in the A. fumigatus Cyp51A gen by using melting curve analysis.

With this state-of-the-art diagnostic approach, it is safe to start with azole monotherapy for the treatment of invasive aspergillosis and the treating physician will not be tempted to change therapy from azole monotherapy to combination therapy because of fear for resistance.

5.4. Escape medication (if applicable)

Not applicable

6. INVESTIGATIONAL PRODUCTS

See also 5.1 and the SPC for more details on anidulafungin, the IP used in this study. Here we describe the findings from non-clinical and clinical studies on combination therapy with a triazole and an echinocandin as combination therapy for the treatment of IA.

6.1. Summary of findings from non-clinical studies concerning triazoles and echinocandins as combination therapy

Findings from non-clinical studies concerning the investigational products show a positive effect of combination therapy in the treatment of IA. A study by Kirkpatrick et al. 15 in which the efficacy of caspofungin and voriconazole combination therapy was evaluated in an immunocompromized guinea pig model of IA, showed a reduced mortality in the combination group compared to the single therapy dosage. In the combination therapy the colony counts were reduced compared to those obtained with either Amfo B alone or voriconazole alone. Only combination therapy resulted in more sterile cultures of organs 96 h after completion of therapy than those achieved with the other therapeutic regimens examined in these experiments. The authors concluded that the combination therapy has relevant clinical importance and the need for further clinical studies to investigate the use of combination therapy for invasive aspergillosis. In a neutropenic rabbit model of invasive pulmonary aspergillosis, the combination of voriconazole and anidulafungin was superior to single agent therapy with respect to mean pulmonary fungal burden and survival, among other measures. 16

6.2. Summary of findings from clinical studies regarding triazoles and echinocandins as combination therapy.

A non-randomized observational study by Singh et al., 2006¹⁷, in which the efficacy of combination of voriconazole and caspofungin as primary therapy for invasive aspergillosis in solid organ transplant recipients was assessed, showed that the survival at 90 days was 67,5% (27/40) in the combination group compared to 51% (24/47) in the L-AmB group, a difference that was not statistically significant. In transplants recipients with renal failure and in those with A. fumigatus infection, combination therapy was independently associated with an improved 90-day survival in multivariate analysis. This study has important limitations as the control group did not receive triazole monotherapy but rather liposomal amphotericin-B as they were treated in the years 1999

and 2002 when voriconazole was not yet available. The only randomized clinical trial in which triazole monotherapy was compared with triazole-echinocandin combination therapy is the study by Marr et al., 2015, in which the efficacy of voriconazole with or without anidulafungin for the treatment of IA in haematology patients was assessed.² Patients were 16 years or older, had an underlying hematologic malignancy and/or had undergone a hematopoietic cell transplantation and were diagnosed with probable or proven IA according to the EORTC/MSG criteria. Patients received either voriconazole and a placebo or voriconazole in combination with anidulafungin. The primary end point was all-cause mortality at 6 weeks after inclusion and one of the secondary endpoints was the 12-week overall mortality. 459 patients were enrolled and were randomly assigned to one of the treatment arms. The miTT population included 277 patients who had confirmed proven or probable IA by the end of the first study week; 135 patients received combination treatment and 142 received monotherapy. The median duration of combination treatment was 14 days (range, 1 to 29); the median duration of voriconazole treatment was 42 days (range, 1 to 48 days). The mortality at 6 weeks in the miTT population was 19.5% (26 of 135) for combination treatment and 27,8% (39 of 142) for monotherapy (with a difference of -8.2%; 95% CI, -,19.0 to 1.5; 2-sided P= 0.087). The mortality at 12 weeks was 29.3% (39 of 135) for the combination treatment and 39.4% (55 of 142) for monotherapy (difference -10.1%; P=0.077). A post-hoc analysis of mortality in the patients with confirmed diagnosis of probable IA that was based on radiographic findings and galactomannan antigen positivity in serum or BAL was performed. All-cause mortality was 15,7% (17 of 108) in the combination therapy group compared with 27,3% (30 of 110) in the monotherapy group (p=0.037). These results were clearly promising and we agree that in real-life a diagnosis of IA in hematology patients is indeed very often based on the combination of a positive galactomannan and pulmonary abnormalities. However, formal conclusions on the value of combination therapy cannot be based on a post-hoc analysis from a single clinical trial. The authors concluded that though results do not provide a conclusive evidence of superiority they add to the support of combination therapy for IA.

6.3. Summary of findings from clinical studies regarding triazole monotherapy

Voriconazole, available as an oral and IV formulation has been the first-line standard of care therapy for patients with invasive aspergillosis since 2003. Indeed, in a pivotal randomized clinical trial in which voriconazole was compared with IV amphotericin-B deoxycholate, the overall 12-week survival was significantly higher in patients treated with voriconazole (71% versus58%).¹

Isavuconazole, available in capsule and IV formulation, is another triazole registered for the treatment of IA. In the large randomized SECURE trial, 527 patients with inva-

sive mold infection were randomized to receive either IV isavuconazole followed by IV or oral (PO) isavuconazole versus IV voriconazole followed by IV or PO voriconazole. The majority of patients in both groups had underlying hematologic malignancy (82% in the isavuconazole group versus 86% in the voriconazole group). The primary endpoint was all-cause mortality at 6 weeks. At 6 weeks, 19% of patients in the isavuconazole group died compared to 20% in the voriconazole group, a difference that did not meet statistical significance. Drug-related adverse events were significantly higher in the voriconazole group compared to the isavuconazole group (60% versus 42%, p < 0.001), and permanent drug discontinuation was lower in the isavuconazole group compared to the voriconazole group (8% versus 14%).¹⁸

Posaconazole, available as tablets and IV formulation, is approved for the use as prophylaxis against invasive fungal infections in patients with acute myeloid leukemie and GVHD. It's in vitro activitity against Aspergillus species is comparable to isavuconazole. A phase III study in which posaconazole is compared with voriconazole is fully enrolled and results are expected in the near future. In patients who cannot tolerate voriconazole and/or isavuconazole, posaconazole is used off-label for the treatment of IA and this is allowed in this trial if the treating physicians things that posaconazole is the best treatment option available for the patient.

6.4. Summary of known and potential risks and benefits

Anidulafungin has an excellent safety profile with reduced toxicities, compared to other licensed antifungal agents. Adverse events that were observed in clinical trials are described in the SPC.

6.5. Description and justification of route of administration and dosage

Anidulafungin will be used at the licensed dose of a 200mg IV loading dose on day 1 and 100mg QD IV thereafter. No dose adjustment is needed in patients with renal or hepatic insufficiency of any grade.

6.6. Dosages, dosage modifications and method of administration

Triazoles

All patients will receive triazole therapy as per standard of care and this will be initiated by the treating physician before the patient is included in the study. Therefore, the triazoles (voriconazole or isavuconazole or posaconazole) are not considered study drugs.

Voriconazole or isavuconazole or posaconazole will be dosed according to the SPC and according to the route of administration (IV or orally) that is preferred by the treating physician. However, the dose may be changed based on therapeutic drug monitoring levels according to the local standard of care.

Anidulafungin:

Anidulafungin (Ecalta) is available as an intravenous formulation only. It will be used at the licensed dose of a 200mg loading dose on day 1 and 100mg QD thereafter. No dose adjustment is needed in patients with renal or hepatic insufficiency of any grade.

6.7. Preparation and labeling of Investigational Medicinal Product

The investigational product will be labeled at the Erasmus MC trial pharmacy according to the relevant good manufacturing practice (GMP) guidelines and with the use of a study label compliant with the Annex 13 EU directive. The investigational products will be shipped to the study sites after labeling and resupplies can be ordered at Erasmus MC.

6.8. Drug accountability

The pharmacy at the study site will carry out the drug accountability. Batch numbers of medication administered to the patients will be recorded in the patient files and CRF. The central pharmacy at Erasmus MC or at the local site will be responsible for the destruction of medication that is returned pursuant to the ICH/GCP Guidelines, local regulations and the investigator's institutional policies. Clinical supplies will be received by a designated person at the study site, handled and stored safely and properly, and kept in a secured location to which only the investigator, a pharmacist or its designated assistant have access. Clinical supplies are dispensed in accordance with the protocol. The investigator is responsible for keeping accurate records of the clinical supplies, the amount dispensed to the ward and returned to the pharmacy by the ward as well as the disposition at the end of the study. The investigator can delegate this task to the hospital pharmacist. A stock of at least 25 vials of 100mg should be in place at the site as long as the study is open for inclusion. If the stock falls below 25 vials, the investigator or the hospital pharmacist will order a new stock of 25 vials, using the order form that will be provided by the Erasmus MC trial pharmacy unit at the time of the first delivery. Ordering more vials is possible after sending a request to the study team ([contact])

7. METHODS

Primary hypothesis

For the treatment of IA, combination therapy of voriconazole or isavuconazole or posaconazole with anidulafungin will improve the overall survival compared with voriconazole or isavuconazole or posaconazole monotherapy.

7.1. Study parameters/endpoints

7.1.1. Main study endpoint

Overall survival 42 days after the start of antifungal therapy in the MITT population

7.1.2. Secondary study endpoints

- 1. Overall aspergillus attributable mortality 12 weeks after the start of antifungal therapy(*).
- 2. Overall survival 12 weeks after the start of antifungal therapy in the MITT population
- 3. Overall survival 6 weeks after the start of therapy in the subgroup of patients in the MITT population with a positive serum galactomannan test at baseline.
- 4. Overall survival 6 weeks after the start of therapy in the subgroup of non-ICU patients who fulfill the EORTC/MSG probable or proven definition (MITT population).
- 5. Overall survival 6 weeks after the start of therapy in the subgroup of non-ICU patients with an underlying haematological disease (MITT population)
- 6. Overall survival 6 weeks after the start of therapy in the subgroup of non-ICU patients without an underlying haematological disease (MITT population)
- 7. Overall survival 6 weeks after the start of therapy in patients that started with triazole monotherapy and in which triazole resistance is detected during follow-up (MITT population)
- 8. Overall survival 6 weeks after the start of therapy in patients that started with triazole-anidulafungin combination therapy and in which triazole resistance is detected during follow-up (MITT population)
- 9. In the subgroup of patients with a positive serum galactomannan; Kinetics of serum galactomannan levels with combination versus monotherapy
- 10. Outcome of patients in which resistance testing was unsuccessful
- 11. Time to hospital discharge (in the MITT subgroup of patients admitted to the hospital at baseline)
- 12. Cost-effectivity of azole-anidulafungin combination therapy
- (*) Aspergillus attributable mortality is defined according to Vidal G et al. (with some modifications) as one of the following²²:

When selecting one of the 4 options below, please consider the immediate cause of death as the disease process, injury, or complication immediately preceding death.

IA is considered the cause of death (=IA attributable mortality)

1. IA was considered the cause of death when the immediate cause of death was due to this infection. Examples are neurological complications of an aspergillus infection

- that disseminated to the brain, lung bleeding or respiratory insufficiency in a patient with pulmonary aspergillosis *or*
- 2. IA was judged to have played a major role if death would not have occurred had the patient not had IA, even though another condition was present that also contributed to death. Examples are toxicity, interactions and other side effects of antifungal treatment that played a major role in the cause of death. Another example is a pseudomonas bacteremia in a patient with a cavitating pulmonary aspergillosis in which the lungs are considered the most likely source of the bacteremia.

IA contributed to the death of the patient: Mortality is not considered attributable to IA but rather contributable if IA or treatment of IA was defined as playing a minor role but probably not essential in explaining the patient's death but arguably did play some role in the event. An example is a patient an aspergillus infection as well as severe uncontrolled gastrointestinal GVHD at the time of death

IA did not contribute nor cause the death of the patient

Mortality was classified as not related to IA if there was a clear other cause of death

Unknown

If insufficient data were present about the circumstances of the death of the patient

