2. OBJECTIVES

Primary objective

1. Evaluate if the survival in patients with a triazole susceptible IA can be improved when the initial therapy consists of triazole and echinocandin combination therapy instead of triazole monotherapy. This objective is captured in the primary endpoint as well as secondary endpoints 1 to 6)

Secondary objectives

- 1. Evaluate if a triazole/echinocandin combination therapy improves the overall quality of life and if it is a cost-effective intervention (these objectives are captured in secondary endpoint 11 and 12)
- 2. Evaluate the outcome of patients in which a triazole-resistant A. fumigatus is detected in relation to the initial antifungal therapy they had received (i.e. triazole monotherapy or combination therapy). This objective translates into secondary endpoint 7 an 8.
- 3. Evaluate the outcome of patients in which resistance testing is unsuccessful in function of the antifungal therapy they received. This translates into secondary endpoint
- 4. Evaluate if the baseline serum galactomannan value and the serum galactomannan kinetics are predictive of overall 6-week survival. This translates into secondary endpoint 3 and 9.

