7.2. Randomisation, blinding and treatment allocation

This is a phase 3 non-blinded non-placebo controlled pragmatic trial. Randomization will be stratified according to the following 3 risk groups: Acute myeloid leukemia, graft-versus host disease and other.

Randomization and concealed allocation will be performed and guaranteed via randomization using blocks of different length and with the use of a randomization module

in the eCRF (Alea). Subjects will be randomized to a 1:1 allocation into 2 treatment group: monotherapy versus combination therapy.

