9.2. Secondary endpoints analyses

The 1st secondary endpoint is defined as attributable mortality at 84 days (12 weeks) follow-up, which will be analyzed in the main analysis population. For this analysis, non-attributable mortality will be considered competing risk for attributable mortality For the analysis of secondary endpoints 2 to 6 see 9.1.

Secondary endpoints 7 and 8 will be analysis using descriptive statistics (6- and 12-week mortality with 95% confidence intervals). If the number of patients in the 2 subgroups described in endpoint 6 and 7 are sufficiently large (\square 25) we will compare the 6 mortality of both groups using the Fisher-Exact test.

Regarding endpoint 9, several studies have studied the impact of galactomannan kinetics on outcome in patients with IA. Studies have shown a reasonable correlation between galactomannan kinetics in the weeks following the initiation of therapy and outcome²¹. However, several questions remain; What is the optimal timing of the follow-up galactomannan measurement? Is the rate of decline more informative than a simpler binary outcome (decline/no decline or decline with 0.5 OD units)? The statistical analysis plan for this endpoint will be written when the study is completed, and the number of galactomannan positive patients and the number of follow-up plasma samples is known.

Secondary endpoints 10 will be analysis using descriptive statistics (6 and 12-week mortality with 95% confidence intervals).

The 11th secondary endpoint is defined as the total duration of the hospital stay. The relation between randomly allocated treatment and this secondary endpoint will be analyzed using a Mann-Whitney U test.

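### Endpoints 7 and 8 group resistant infections by therapy begun and by open-ended detection, in a population that excludes them, so the conditional comparison in 9.2 is open to bias

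*Protocol*

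**What the plan says.** Protocol section 7.1.2 sets endpoint 7 as 6-week overall survival in "patients that started with triazole monotherapy and in which triazole resistance is detected during follow-up". Endpoint 8 is the same for patients who began on triazole plus anidulafungin. Both carry the MITT label. They serve secondary objective 2 (section 2), which looks at outcome in resistant infection "in relation to the initial antifungal therapy they had received".

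On timing of treatment, section 6.6 says of triazole therapy that "this will be initiated by the treating physician before the patient is included in the study". Exclusion criterion 5 (section 4.3) rules out earlier azole or echinocandin treatment of the episode only beyond 96 hours.

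On allocation, section 7.2 states: "Subjects will be randomized to a 1:1 allocation into 2 treatment group: monotherapy versus combination therapy". The trial is not blinded.

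On analysis, section 9.2 describes 6- and 12-week mortality in the two groups with 95% confidence intervals. If the groups are large enough (a threshold of 25), it adds: "we will compare the 6 mortality of both groups using the Fisher-Exact test". That sentence refers to endpoints 6 and 7, not 7 and 8.

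**The concern.** Three features of the definition weaken the comparison that is meant to answer objective 2.

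- **Grouping.** The therapy a patient began on can differ from the arm the patient was allocated to. A comparison by therapy begun is protected by randomisation only where the two coincide.
- **Detection.** Resistance found at any time in follow-up qualifies. Whether and when a patient is resampled can depend on how that patient is doing and, in an open-label trial, on the known treatment.
- **Population.** The label names a population from which resistant infections have been removed.

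A mortality difference between the groups could then partly reflect who was sampled and when. Two analysts working from this text could also build different groups.

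**Working it through.** **1. The plan's own figure.** Endpoints 7 and 8 have no sample size of their own. The primary figure in section 9.5 reproduces. With p1 = 0.35, p2 = 0.2333, two-sided alpha 0.05, power 0.80 and mean rate p = 0.29165, n = [1.960·√(2p(1−p)) + 0.842·√(p1(1−p1)+p2(1−p2))]² / (p1−p2)² = 237 per group. It is used below only to gauge how many resistant infections to expect.

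**2. Grouping.** Section 6.6 puts the triazole before inclusion, and section 7.3 has all patients on it at screening. Inclusion criterion 2 (section 4.2) also allows a start at the baseline visit, and Appendix 2 puts screening and baseline on the same day with few exceptions. Sections 1 and 5.3 report that Dutch guidance offers upfront combination therapy as an option. So a combination-arm patient may have begun on a triazole alone, and a control patient may have begun on a combination. The documents do not say how often either occurs.

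**3. Detection.** Endpoint 3 is fixed at baseline, and section 7.1.4 gives the qualifying mycological test 8 days after randomisation. Resistance in endpoints 7 and 8 has no limit, while follow-up runs to week 24 (section 7.3, Appendix 2). A patient first found resistant in a sample taken after day 42 was alive to be sampled, so cannot count as a 6-week death.

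**4. Population.** Section 7.1.4 removes documented voriconazole resistance from the MITT. Section 5.1 says patients with demonstrated triazole resistance are not in the MITT primary endpoint population. Under the MITT label the expected number in each group is zero.

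**5. Could the Fisher test be triggered?** Suppose the groups come from all randomised patients and 25 is needed in each (the sign before 25 is lost in the text; read as at least). If every patient has a result and a share r is resistant, 237 susceptible patients per arm imply 237·r/(1−r) resistant ones. If instead 35% have no interpretable result (section 1) and all of those stay in the MITT, the count is 237·0.65r/(1−0.65r).

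| r | All have a result | Chance both arms reach 25 | 35% without result |
|---|---|---|---|
| 5% | 12.5 | about 0 | 8.0 |
| 10% | 26.3 | 0.40 | 16.5 |
| 13% | 35.4 | 0.96 | 21.9 |
| 15% | 41.8 | 0.998 | 25.6 |

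The chances apply to the second column. Section 1 reports 15% for the Netherlands, and 5% for Belgium with 13% in one hospital; 10% is an assumed midpoint. The test is a real possibility at the higher prevalences.

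**6. Possible size of the distortion.** All inputs here are assumed except the 50–88% mortality range for resistant infection, which section 1 gives for initially inappropriate voriconazole.

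- *Upward, by detection.* Let true mortality m be equal in both arms. In one arm, detection is 100% in patients who die and 65% in survivors; in the other it does not depend on outcome. Observed mortality in the first arm is m / (m + 0.65(1−m)):
  - m = 0.50: 0.50/0.825 = 60.6% (+10.6 points)
  - m = 0.70: 0.70/0.895 = 78.2% (+8.2)
  - m = 0.88: 0.88/0.958 = 91.9% (+3.9)
- *Upward, by adding failing patients.* 20 patients found at entry with 40% mortality plus 10 found while failing with 80%: (8 + 8)/30 = 53.3% (+13.3 points).
- *Downward, by late detection.* 20 patients with 50% mortality plus 5 first sampled positive after day 42: 10/25 = 40%. With 10 such patients: 10/30 = 33.3%. That is 10 to 16.7 points lower.
- *No distortion.* If detection does not depend on outcome, or does so equally in both arms when true mortality is equal, the spurious difference is 0.

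**The case against.** A reader might infer that the comparison is not randomised and is biased. The documents do not support that.

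- The primary objective also speaks of initial therapy, and there it plainly means the randomised regimen. Objective 2 names the same two options as the arms in section 7.2. The natural intent is grouping by arm.
- Nor does it follow that nearly every combination-arm patient would fall under endpoint 7, since a same-day triazole start is allowed.
- Resistance belongs to the infecting strain and is normally read from the diagnostic BAL sample (section 5.3). No repeat respiratory sampling is scheduled, and no testing rule differs by arm. If testing is alike in both arms, a comparison by allocated arm keeps its randomisation.
- The analysis is mainly descriptive and the test is conditional. The magnitudes above rest on invented counts and detection rates and point both ways.

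All of this stands, and it limits the claim to a definition that is open to bias. It does not remove the point. A sampling cut-off might ordinarily be left to the SAP, but here the protocol itself states a rule, detection during follow-up, which read literally admits guaranteed 6-week survivors and resampling driven by clinical course. Testing is also only offered at Belgian sites where it is not standard (section 5.3), so uniform detection is not assured. The conflict with the MITT definition does not depend on any of these arguments.

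**Conclusion.** The point holds as a defect of definition; bias is not demonstrated. Two parts rest on the text alone: the MITT label contradicts sections 5.1 and 7.1.4 and leaves the groups empty, and section 9.2 cites the wrong endpoint pair. The other two, grouping by therapy begun and detection without a time limit, leave the conditional comparison open to bias of unknown size and direction. A spurious between-arm difference needs grouping or detection to differ between the arms; the documents neither show this nor rule it out. The endpoints are secondary and the primary analysis is untouched, but section 2 names them as the translation of objective 2, so the wording should be corrected before analysis.

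**What to change.** Reword endpoints 7 and 8, objective 2 and the matching sentence in section 9.2:

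- **Population and grouping:** all randomised patients (the ITT population of section 7.1.4), by allocated arm. Drop the MITT label.
- **Resistance:** documented in samples collected up to 8 days after randomisation. This borrows the length of the mycology window in 7.1.4 but applies it to the collection date. A cut-off at randomisation should not be the main rule, because inclusion criterion 7 admits some patients before mycology is known, and their BAL may follow randomisation.
- **Sensitivity set:** resistance in samples taken up to randomisation.
- **Later samples:** report resistance first found after the window descriptively, outside the between-arm comparison.
- **Cross-reference:** change endpoints 6 and 7 in section 9.2 to 7 and 8.

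The cost is wording only, with no new data, provided sample collection dates are on record. The downside is that a few late-detected patients move to a descriptive table.
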